2. INTRODUCTION

The purpose of this Registry is to detect any major teratogenic effect in pregnancies intentionally or unintentionally exposed to Twinrix. The combination of the large number of women who are of reproductive capacity and live in hepatitis A- and hepatitis B-endemic areas, and the lack of data concerning exposure to Twinrix during pregnancy makes such a Registry an important component of the ongoing program to assess the safety of Twinrix. This is a prospective, voluntary, observational, exposure-registration study. Patient confidentiality will be strictly maintained. The purpose of the Registry is to prospectively collect data describing exposure to Twinrix before or during pregnancy, potential confounding factors (such as exposure to other medications), and information related to the outcome of the pregnancy. The Registry is intended to provide an early signal of potential risks in advance of results from formal epidemiologic studies. Registry data are used to supplement animal toxicology studies and to assist clinicians in weighing the potential risks and benefits of treatment for individual patients.

The Twinrix Pregnancy Registry will be maintained by Biological Clinical Safety and Pharmacovigilance. Enrollment in the Registry will begin at the time of commercial launch of Twinrix in the US. At the time of initiation of the Registry, pre-existing reports of pregnancy from clinical trials will be evaluated and enrolled when the criteria for registration are met.

3. METHODS

3.1. Registration and Follow-up

Reporting of exposed pregnancies is voluntary. Pregnancies will be registered following maternal exposure to Twinrix within 28 days prior to conception or during pregnancy. Registration of pregnancies is prospective, i.e., reported during pregnancy before the pregnancy outcome is known. Retrospective reports, i.e., those for which the outcome is known at the time of registration, will also be reviewed. However, because retrospective reports are more likely to be biased by relatively more frequent reporting of abnormal outcomes, such reports are less likely to be representative of the general population experience and, therefore, cannot be used for risk assessment or analysis [Mitchell, 1988 and Wilcox, 1984]. Health care providers with patients exposed to Twinrix during pregnancy will be encouraged to enroll their patients in the Registry as early in the pregnancy as possible to maximize the validity of the study. Health care providers can enrol their patients by calling the telephone number PPD [REDACTED].

When the pregnancy is reported prospectively, the Registry will collect registration data from the reporter through telephone interview or a short registration form. In the

CONFIDENTIAL

month of the estimated date of delivery follow-up will be sought by telephone contact or a form mailed to the health professional. Information about maternal events throughout the pregnancy, pregnancy outcome, and neonatal health is requested. Additional follow-up is not sought from subsequent health care providers.

A report of an exposure will be closed when clear information is received about exposure to Twinrix and pregnancy outcome determination, or when the patient is lost to follow-up. A patient is considered to be lost to follow-up when the Registry does not receive the minimum information, or if the reporting health care provider can no longer locate the patient. Only data from “closed” reports of exposed pregnancies with known outcomes will be considered for analysis.

3.2. Inclusion criteria

For a pregnancy report to be considered eligible for registration, certain data must be available. The required data include:

- Documentation that Twinrix was administered \leq 28 days before or during pregnancy;
- Confirmation that the pregnancy is being prospectively reported;
- Report made by a patient or a health care professional;
- The timing of the prenatal exposure to Twinrix (no broader than during which trimester);
- A patient identifier that will allow follow-up to be obtained so that the pregnancy outcome can be ascertained;
- Whether the patient was involved in a clinical trial at the time of the exposure;
- Full reporter contact information.

3.3. Classification of Outcomes

This Registry uses the term "birth defects" for outcomes sometimes referred to as “congenital anomalies.” For purposes of analysis, pregnancy outcomes will be dichotomized according to the presence or absence of birth defects. The latter group will be further categorized as: 1) Live births, 2) spontaneous abortions (i.e., pregnancy losses), and 3) induced abortions. This Registry has adopted a definition of a child with a birth defect as any live or stillborn neonate with a structural or chromosomal abnormality diagnosed before 6 years of age. The Registry will employ a conservative approach of including all defects, including minor ones, as congenital abnormalities. Therefore, conditions not appearing in the Centers for Disease Control and Prevention (CDC) Inclusion List may be classified as congenital abnormalities. All defects will be included in the “congenital abnormalities” category, regardless of whether or not the neonate is delivered alive, including structural defects in neonates delivered prior to 20 weeks of gestation or weighing less than 500 grams. However, CDC guidelines

disqualify as defects those findings that are present in infants delivered at less than 36 weeks of gestation and are attributable to prematurity itself, such as a patent ductus arteriosus or inguinal hernias. Infants with infectious conditions (e.g., neonatal sepsis) or biochemical abnormalities (e.g., hyperbilirubinemia) will be classified as being without congenital abnormalities unless there is a possibility that the condition reflects an unrecognized birth defect.

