3.5. Analysis

Pregnancy outcomes will be stratified by the trimester of exposure, with an additional stratum for preconception exposure with no subsequent administration during pregnancy. Reports of multiple exposures (i.e., multiple administrations of Twinrix) during a pregnancy will be classified by the earliest trimester of exposure. When exposure occurs before and after conception, the exposure will be classified by the dose administered after conception. Gestational weeks will be counted from the date of the last menstrual period. The second trimester will be considered to begin at week 14, and the third trimester beginning at week 28.

The calculations of risk for birth defects will be made by dividing the number of infants with birth defects by the total number of infants with and without birth defects. Spontaneous abortions and induced abortions not including birth defects will be excluded from this calculation. An exact 95% confidence interval (CI) will be calculated using the software application Stata, version 8.2 (Stata Corporation, College Park, TX).

The risk in the general population of all birth defects meeting CDC criteria is approximately 3% (range 2%-5%) of live births [Centers for Disease Control]. The estimated risk cited in medical literature varies because of differences in case definitions, populations sampled, and ascertainment methods. The Collaborative Prenatal Project, using a broader case definition and prospective ascertainment, reported a frequency of 5-7% [Chung, 1975]. Most major structural defects originate during the first trimester of pregnancy, which is the critical time for organogenesis. For such defects, exposures occurring in the second or third trimester are not likely to be causally associated. However, for the sake of completeness, and to enable the

CONFIDENTIAL

assessment of possible increases in the frequency of birth defects, all defects will be included in the reports for this Registry.

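### Only an all-defects risk is planned, so the cited 3% of live births (CDC criteria) has no comparable registry estimate, and aggregate criterion 1 names no background figure

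*Combined protocol and SAP*

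**What the plan says.** **Case definition (protocol, section 3.3).** A child with a birth defect is "any live or stillborn neonate with a structural or chromosomal abnormality diagnosed before 6 years of age". The section adds: "The Registry will employ a conservative approach of including all defects, including minor ones, as congenital abnormalities". It accepts that conditions absent from the CDC Inclusion List may count. Defects count "regardless of whether or not the neonate is delivered alive", including structural defects before 20 weeks or below 500 g. CDC guidelines are cited to disqualify findings due to prematurity before 36 weeks.

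**Risk formula (section 3.5).** Risk is obtained by "dividing the number of infants with birth defects by the total number of infants with and without birth defects", with an exact 95% CI. On losses: "Spontaneous abortions and induced abortions not including birth defects will be excluded from this calculation". Losses with a defect therefore stay in. Outcomes are stratified by period of exposure. No second case definition is analysed.

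**Background figures (section 3.5).**
- "The risk in the general population of all birth defects meeting CDC criteria is approximately 3% (range 2%-5%) of live births".
- A second source, "using a broader case definition and prospective ascertainment, reported a frequency of 5-7" per cent.
- Between the two: "The estimated risk cited in medical literature varies because of differences in case definitions, populations sampled, and ascertainment methods".

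**Use of the background.** The first criterion for aggregate data in section 3.5 asks whether the frequency of all defects deviates from what is expected, without giving a number or a source. Section 1 says only that a comparison with the literature is possible.

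**The concern.** The 3% figure differs from the registry risk in case definition: CDC criteria on one side, and every defect, including minor and non-listed ones, on the other. It is also expressed per live births, while the registry's cases need not be live-born. No planned estimate uses CDC criteria, so nothing the registry reports can be set against 3% on like terms.

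The two cited figures differ by a factor of 5/3 = 1.7 to 7/3 = 2.3. The same registry count can look raised against one and unremarkable against the other. Section 3.6 schedules reviews at six and twelve months and then yearly. Each would have to settle the choice of reference afresh, possibly after seeing the data.

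**Working it through.** **Side by side.**

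| Feature | Registry risk (3.3, 3.5) | 3% (2%-5%) figure (3.5) | 5-7% figure (3.5) |
|---|---|---|---|
| Case definition | all defects, minor and non-listed included | CDC criteria | described as broader; minor defects not mentioned |
| Cases not born alive | counted | not stated for the numerator | not stated |
| Base | infants with and without defects | live births | not stated |
| Ascertainment | follow-up sought in the month of expected delivery (3.1) | not stated | prospective; age not stated |
| Assigned to criterion 1 | not applicable | no | no |

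The mismatch in case definition with the 3% figure follows from the text alone and needs no assumption.

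**Size.** The plan gives no sample size, test or threshold, so there is no figure of its own to reproduce. Everything below is an illustration that assumes (a) n infants and (b) the rule that the exact 95% lower limit must exceed the reference.

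Exact limits for x cases in n, as Beta quantiles:
- lower = Beta(0.025; x, n − x + 1)
- upper = Beta(0.975; x + 1, n − x)

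Example: x = 12, n = 200 gives 12/200 = 6.0%, with limits 3.14% and 10.25%. The interval is above 3% and contains all of 5-7%.

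Smallest count whose lower limit exceeds each reference:

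| n | above 3% | above 5% | above 7% |
|---|---|---|---|
| 100 | 8 | 11 | 13 |
| 200 | 12 | 17 | 22 |
| 500 | 24 | 36 | 48 |

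Counts that exclude 3% but not 5% are therefore 8-10 of 100, 12-16 of 200 and 24-35 of 500.

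Next, suppose there is no vaccine effect and the true all-defects risk is 6%, the midpoint of 5-7%. With r the count in the table, the chance of crossing is P(X ≥ r), X ~ Binomial(n, 0.06):

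| n | lower limit above 3% | lower limit above 5% |
|---|---|---|
| 100 | 25% | 3.8% |
| 200 | 54% | 9.5% |
| 500 | 89% | 15% |

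If the true risk is 5% or 7% instead, the chance of crossing 3% is 13% or 40% at n = 100, 30% or 75% at n = 200, and 61% or 98% at n = 500.

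The last column matters because 5% is both the top of the 2%-5% range and the bottom of 5-7%. Against the full range the conflict is much smaller than against the 3% point.

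**The case against.** The strongest reply is that the plan is open about all of this. Section 3.3 calls its definition conservative and says that it goes beyond the CDC list. Section 3.5 states the criteria and base of the 3% figure, explains why published estimates differ, and offers a second figure under a broader definition. All defects are reported, cases are reviewed individually, and frequencies of individual defects are a separate criterion. Reporting is voluntary and the plan states no test, so any comparison is descriptive.

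Most of that stands, and it keeps the point small. It does not supply a pairing of either figure with the registry risk, or a registry estimate on CDC criteria. Frequencies of single defects do not give an overall CDC-criteria risk.

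A reader might infer four stronger things that the documents do not support:

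- **That criterion 1 will be judged against 3%, so false alarms are built in.** No sentence says so. The percentages above describe what would happen if it were.
- **That 5-7% is the matched reference.** It looks closer, but the documents do not say whether that source counted minor defects or cases not born alive.
- **That the live-birth base by itself shifts the result.** Changing only the denominator barely matters: 12/199 = 6.03% has lower limit 3.15%, against 3.14% for 12/200. Removing one case from the numerator does matter: 11/200 = 5.5% has lower limit 2.78%. Whether the 3% figure counts cases not born alive is not stated.
- **That follow-up around delivery, against a definition reaching age 6, pulls the registry risk below a comparable 3%.** It may miss later diagnoses, but no ascertainment age is given for the 3% figure, so the effect on the comparison is unknown.

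**Conclusion.** The point holds as a minor one. The registry's single risk estimate has no like-for-like relation to the 3% figure, and criterion 1 has no designated background. The definitional part rests on the text alone. The numerical part rests on assumed n, an assumed decision rule and an assumed true risk of 5-7%. Within those assumptions the choice of reference can decide how a review reads, as with 12 of 200. Nothing here invalidates the registry or loses information that it collects. It is a cheap improvement in how the aggregate comparison is set up.

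**What to change.** **Section 3.3.** Code each reported defect as meeting CDC criteria or not, using the CDC list and guidelines already cited there.

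**Section 3.5.**
1. Keep the all-defects risk unchanged.
2. Add a CDC-criteria risk per live births with an exact 95% CI. Show it with and without non-live-born CDC-criteria cases in the numerator, because the documents do not say whether the 3% figure includes them. Compare it with 3% and with the 2%-5% range.
3. Show the all-defects risk beside 5-7%, described as the closer but not demonstrably matched reference.
4. State that criterion 1 is judged on both comparisons together.
5. Note beside both that follow-up is sought around delivery, that reporting is voluntary, and that the comparisons are descriptive.

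**Cost.** One coded field per defect and a few sentences. There are two real downsides:
- The second estimate is sparser. For example, 6/200 (3.0%) has exact CI 1.11%-6.42%, an upper-to-lower ratio of 6.42/1.11 = 5.8, against 10.25/3.14 = 3.3 for 12/200.
- Reading the all-defects risk against 5-7% instead of 3% means more cases are needed to stand out under the assumed rule: 17-22 instead of 12 of 200, and 36-48 instead of 24 of 500. Section 2 wants an early signal, which is why the CDC-criteria comparison with 3% should be kept alongside.

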3.4. Exclusions

For this Registry, emphasis is placed on prospective registration of pregnancies. Although the Registry will encourage reporting of all known prenatal exposures to Twinrix, not all reports are appropriate for inclusion in the analysis of data.

Retrospective reports from patients and health care providers will also be received in the Registry. These outcomes will be reviewed and are helpful for detecting a possible pattern of defects. However, because there is no denominator from which risk can be calculated, these reports will be excluded from the analysis, although they will be summarized in the registry reports.

3.5. Analysis

Pregnancy outcomes will be stratified by the trimester of exposure, with an additional stratum for preconception exposure with no subsequent administration during pregnancy. Reports of multiple exposures (i.e., multiple administrations of Twinrix) during a pregnancy will be classified by the earliest trimester of exposure. When exposure occurs before and after conception, the exposure will be classified by the dose administered after conception. Gestational weeks will be counted from the date of the last menstrual period. The second trimester will be considered to begin at week 14, and the third trimester beginning at week 28.

The calculations of risk for birth defects will be made by dividing the number of infants with birth defects by the total number of infants with and without birth defects. Spontaneous abortions and induced abortions not including birth defects will be excluded from this calculation. An exact 95% confidence interval (CI) will be calculated using the software application Stata, version 8.2 (Stata Corporation, College Park, TX).

The risk in the general population of all birth defects meeting CDC criteria is approximately 3% (range 2%-5%) of live births [Centers for Disease Control]. The estimated risk cited in medical literature varies because of differences in case definitions, populations sampled, and ascertainment methods. The Collaborative Prenatal Project, using a broader case definition and prospective ascertainment, reported a frequency of 5-7% [Chung, 1975]. Most major structural defects originate during the first trimester of pregnancy, which is the critical time for organogenesis. For such defects, exposures occurring in the second or third trimester are not likely to be causally associated. However, for the sake of completeness, and to enable the

CONFIDENTIAL

assessment of possible increases in the frequency of birth defects, all defects will be included in the reports for this Registry.

Criteria for review of a specific individual report include: 1) was the timing of the exposure to Twinrix commensurate with the ontogenetic development of the organ(s) affected by the abnormalities; 2) was there another known or likely cause (e.g., preexisting genetic or chromosomal defect or exposure to a known teratogen); 3) was the congenital abnormality not previously described (i.e., was it new to medical science); 4) was there a unique constellation of defects (i.e., was there a new syndrome)? Criteria for review of aggregate data include: 1) was there a deviation from the expected frequency of all defects indicating an increase in the overall risk of defects; 2) was there a deviation from the expected frequencies of individual defects; 3) was there uniqueness (e.g., a pattern) of the abnormalities that is suggestive of a common etiology? Studies have shown the risk of spontaneous abortion is high early in pregnancy and decreases substantially from week 8 to week 28, yielding a cumulative estimated risk of 10-22% [Anderson, 2000, Fenster, 1997, Khattak, 1999, Osborn, 2000, Ventura, 2000, Wilcox, 1981, Wilcox, 1983, Wilcox, 1988, and Windham, 1997]. Calculation of risk of spontaneous pregnancy losses overall should not be attempted and cannot be compared to the incidence in the general population because pregnancies in this Registry are reported at variable and, occasionally, imprecise times. Also, pregnancy losses occurring early in gestation may not be recognized and/or reported.

While the Registry is limited to prospective reports, some pregnancy exposures are reported only following pregnancy outcome (retrospective reports). The Registry will also review each retrospective report involving a birth defect. In general, retrospective notification of outcomes following exposures to drugs or vaccines is biased toward reporting the severe and unusual cases, and is not reflective of the general experience with the drug. Moreover, information about the total number of exposed persons is unknown. Therefore, incidences of outcomes cannot be calculated from these data. However, a series of reported birth defects can be analyzed to detect patterns of specific congenital abnormalities and can identify early signals of new vaccine-associated risks. A separate section of each registry report will describe all abnormal outcomes of retrospectively reported cases.

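### Trimester-of-exposure strata are truncated differently by survival to the dose, so defect risk tends to be higher for earlier exposure even with no vaccine effect

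*Combined protocol and SAP*

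**What the plan says.** All references are to the combined protocol and SAP.

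- **Strata (3.5).** "Pregnancy outcomes will be stratified by the trimester of exposure"; women dosed only before conception form one more stratum. A pregnancy with several doses "will be classified by the earliest trimester of exposure". Weeks run from the last menstrual period: "The second trimester will be considered to begin at week 14, and the third trimester beginning at week 28".
- **Risk (3.5).** It is obtained by "dividing the number of infants with birth defects by the total number of infants with and without birth defects", with an exact 95% CI. Spontaneous and induced abortions without a defect are left out. Section 3.7 describes the exclusion in the same way, so losses and terminations with a reported defect stay in.
- **Defects that count (3.3).** All defects count, in live and other deliveries alike, "including structural defects in neonates delivered prior to 20 weeks of gestation or weighing less than 500 grams".
- **Entry (3.1).** Only reports made before the outcome is known are analysed. Providers are encouraged to "enroll their patients in the Registry as early in the pregnancy as possible to maximize the validity of the study".
- **Reading of the later strata (3.5).** For most major structural defects, "exposures occurring in the second or third trimester are not likely to be causally associated".
- **Limits already stated.** Sections 1 and 3.5 say that spontaneous-abortion risk should not be calculated, because pregnancies are reported at variable times. Section 1 gives an example of a pregnancy recognised at week 10. Section 3.7 says that leaving out defect-free losses may introduce bias. Neither point is carried over to differences between strata in the birth-defect risk.

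**The concern.** To be in the third-trimester stratum, a pregnancy must still be ongoing at a first in-pregnancy dose given at week 28 or later. To be in the second, it must have reached at least week 14. The numerator includes defects found in pregnancies that end earlier than that. One formula therefore measures different quantities: the preconception and first-trimester strata can include early-ending defect cases, the second only those ending from week 14 on, and the third none ending before week 28.

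Defect-free losses leave both numerator and denominator, so nothing offsets the early-ending defect cases. They raise the risk wherever they can be seen.

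The registry has no control group, and the plan calls later exposure an unlikely cause of most major structural defects. A reader may well treat the later strata as an informal reference and take a higher first-trimester risk as the signal the registry exists to detect. More years of reports narrow the intervals but do not remove this component.

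Delayed reporting acts in the opposite direction. A first-trimester exposure reported at week 30 has already escaped the early endings. The plan links early enrolment to validity but does not analyse by time of report.

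**Working it through.** The plan states no stratum-specific expected risk, sample size or power, so there is no figure to reproduce. The check asks what each stratum would show with no vaccine effect.

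**1. Which endings each stratum can hold (from 3.3 and 3.5)**

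| Defect-positive ending | Preconception / first | Second | Third |
|---|---|---|---|
| Before week 14 | possible | impossible | impossible |
| Weeks 14-27 | possible | possible, if dosed before the ending | impossible |
| Week 28 on | possible | possible | possible, if dosed before the ending |

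For example, a first dose at week 15 followed by a loss at week 18 with a structural defect is a second-trimester case that 3.3 counts.

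**2. Size if every first-trimester exposure is reported early**

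Inputs: p = all-defects risk including early endings, taken as 5% (3.5 gives about 3%, range 2%-5%, of live births, and 5-7% under a broader definition). x = share of affected pregnancies that end before week 28 with the defect recognised, taken as 10%-30%. The choice of p and all of x are assumptions. Defect-free infants in the calculation are taken to be delivered after week 28.

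First-trimester risk = p. Third-trimester risk = p(1-x) / [p(1-x) + 1 - p].

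- x = 0.1: 0.045/0.995 = 4.52%; ratio 5.00/4.52 = 1.11
- x = 0.2: 0.040/0.990 = 4.04%; ratio 1.24
- x = 0.3: 0.035/0.985 = 3.55%; ratio 1.41

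At p = 3% the ratios are 1.11, 1.24 and 1.42.

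**3. Allowing for late reports**

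Let a share L of first-trimester exposures be reported only after the early-ending window. Their risk equals the third-trimester risk. If R is the ratio from step 2, the ratio becomes (1-L)R + L.

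- x = 0.1, L = 0.6: 0.4 × 1.106 + 0.6 = 1.04
- x = 0.3, L = 0.2: 0.8 × 1.407 + 0.2 = 1.33
- L = 1: 1.00 for any x

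**4. Second trimester, with a week-by-week model**

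Let b = 3% be the risk without early endings, e the recognised defect-positive endings before week 28 per birth, and S the average share of those endings still ahead at entry. Risk = (b + eS)/(1 + eS). Assume e = 1%, endings split 35/40/25 over weeks 6-13, 14-19 and 20-27, and entry at the dose, spread evenly over each trimester.

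- First: S = 0.898; 0.03898/1.00898 = 3.86%
- Second: S = 0.2875; 0.032875/1.002875 = 3.28%
- Third: S = 0; 3.00%

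The first-to-third ratio is 1.29. With e from 0.2% to 2% and three different timing splits, it runs from 1.05 to 1.62.

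Moving entry from the dose to the report (e = 1%, same split), first-trimester exposures show 3.81% if reported at weeks 6-13, 3.54% at weeks 10-20 and 3.10% at weeks 20-30. Second-trimester exposures reported at weeks 18-30 show 3.14%. The fall from first to second can therefore vanish or slightly reverse.

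**5. Effect of a common landmark**

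Restricting every stratum to deliveries at or after week 28 removes the early endings from each. In step 2 the first-trimester risk becomes p(1-x)/[p(1-x) + 1 - p], the same as the third, so the ratio is 1.0. In step 4 every stratum gives 3.0%.

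**The case against.** The strongest reply is that the plan makes no between-trimester comparison. Section 1 names the medical literature as the possible comparator, and the aggregate criteria in 3.5 are departures from expected frequencies and patterns of defects. The sentence on second- and third-trimester exposure leads into why all defects are still reported; it does not make later strata internal controls. Chance would usually swamp the gap: at 80% power and two-sided 5%, telling 5.0% from 3.55% needs about 3,100 per stratum, and 5.0% from 4.5% about 31,000. This stands. It makes the point one of interpretation, not a faulty test, and lowers its weight.

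The gradient is also conditional. Entry is at the report, not the dose, and 3.7 accepts that anomalies may not be known to the reporting physician. Where early defects go unrecognised or early exposures are reported late, the gap shrinks or disappears. This stands too.

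Two stronger readings are tempting. A reader might infer that only the preconception and first-trimester strata can hold the early-ending defects that 3.3 counts. That is exact only for endings before week 14, because the second-trimester stratum begins there and 3.3 counts structural defects in deliveries before 20 weeks. A reader might also infer that the risks must fall from each stratum to the next. The documents do not support that: preconception and first-trimester exposures both enter only when the pregnancy is known and reported, and late reporting can cancel the first-to-second fall.

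The objection does not remove the structural point. The strata are shown under one risk definition although their eligible outcomes differ, and the limits disclosed in Sections 1, 3.5 and 3.7 do not say so for birth defects.

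**Conclusion.** The concern holds as a tendency. With no vaccine effect, earlier-exposure strata can show a higher defect risk, because the later strata exclude defect-positive pregnancies that ended before the dose could be given. The exclusion is exact before week 28 for the third-trimester stratum and before week 14 for the second.

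On the assumptions in steps 2 and 3, the size lies between no gap (all early exposures reported late) and a ratio of 1.41 (all reported early), with about 1.04-1.33 in between. The early-ending share, its timing and the reporting delay are not in the documents, so these figures illustrate and do not predict. The consequence is a possible misreading of a first-trimester excess; no stated test is invalidated. Nor is the all-outcome first-trimester risk wrong as a description of that stratum; it is simply not on the same footing as the later ones.

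**What to change.** In 3.5:

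1. Keep the all-outcome risk for each stratum. Whenever strata are shown together, also give each stratum's risk, with exact 95% CI, among infants, live or stillborn, delivered at or after 28 weeks. Restrict numerator and denominator alike, and say that defect-free stillbirths count in the denominator, since 3.3 lists no such category. Base any between-trimester statement on this figure.
2. Record gestational age at report, or derive it from the estimated delivery date that 3.1 already uses to time follow-up. The eligibility data in 3.2 require exposure timing only to the trimester and do not list it. Show the preconception and first-trimester risks separately for reports before week 28 and at or after week 28, matching the landmark.

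The cost is SAP wording, one extra table and possibly one recorded item. The restricted figure drops early-ending defects and is slightly less precise, which is why the all-outcome risk must stay. It also leaves a small residual truncation: a dose at week 35 still requires survival to week 35.
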